7.2.4 Study Visit 3 – 4 week treatment

The subject will return in 4 weeks for a follow up visit. The study visit window will be 3 days before or 3 days after this time to account for weekends. At this time the subject will be given time to ask any questions or voice any concerns they may have had over the past 4 weeks, reviewing and recording any adverse events. The subject's compliance with daily surveys and study drug will be reviewed.

A physical assessment will be performed as detailed in Section 7.2.3. Subjects who experience severe adverse events will be instructed to stop the study drug and withdraw from the study. Please refer to Section 3.3.1.

The subject will be given another 1 month supply of the study drug and NETA as needed. As stated above, NETA dosage will be adjusted as necessary.

The subject will also complete the following surveys: (1) EHP-30 (2) PGA (3) PGIC (4) C-SSRS (5) FSFI (if partnered and sexually active) on-site prior to being discharged from the visit. The following bloodwork will be obtained: (1) Inflammatory markers (2) Monitoring LFTS. Approximately 1-2 teaspoons of blood will be drawn at this visit.

They will be required to bring all medication bottles to the visit. Oxycodone, if prescribed, and NETA pills will be counted and recorded. Additional refills will be provided as needed. The study drug bottle and NETA will be inspected and returned to the clinician. The patient will be provided with a new supply of study drug and NETA at this time.

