1.0 Objectives

1.1 Study Objectives

Our central hypothesis is that Cannabidiol will result in a significant improvement of endometriosisrelated pain. This proposal seeks to (1) determine if cannabidiol will result in an overall improvement of patient-reported endometriosis associated pain (2) determine if this pain reduction is dose-dependent (3) determine if cannabidiol will result in improved sexual function (4) determine if cannabidiol will result in an overall improved quality of life among women with endometriosis (5) determine if CBD affects common inflammatory markers associated with endometriosis (6) to determine the pharmacokinetics of sublingual CBD. We propose a randomized double-blind placebo-controlled pilot study to achieve the following aims:

Aim 1: Identify the overall impact of cannabidiol (CBD) on endometriosis related pain. We plan to measure endometriosis related pain using daily self-reported Visual Analogue Scale (VAS) scores over an 8 week period.

Aim 2: Identify the dose-dependent impact of cannabidiol on endometriosis related pain. We will be dividing our patients into 3 arms – high dose CBD, low dose CBD and placebo. We plan to measure and compare endometriosis related pain using daily self-reported Visual Analogue Scale (VAS) scores.

Aim 3: Identify the overall impact of cannabidiol (CBD) on sexual function. This will be assessed via the Female Sexual Function Index (FSFI), a validated survey, to be administered to participants with current sexual partners that are sexually active.

Aim 4: Identify the impact of cannabidiol on Quality of Life (QOL) among women with endometriosis. We plan to measure QOL using the Endometriosis Health Profile-30 (EHP30), Patient Global Assessments (PGAs), and Patient Global Impression of Change (PGIC) surveys. These are validated health surveys.

Aim 5: To measure inflammatory cytokines that have been linked to the pathogenesis of endometriosis and to determine if CBD will alter these inflammatory markers.

Aim 6: On a small subset of patients (4), we will study the pharmacokinetics of sublingual CBD.

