1.3 Secondary Study Endpoints

- (1) To determine the difference in QOL measurements between study groups. The EHP30 is a validated survey used to measure quality of life outcomes in women with endometriosis. PGIC and PGAs are routinely used in endometriosis clinical trials to assess outcome measures such as dysmenorrhea, non-menstrual pelvic pain and dyspareunia.
- (2) To identify the overall impact of CBD on sexual function among participants that are currently partnered and sexually active.
- (3) To measure inflammatory cytokines and determine their levels before, during and at the end of the treatment cycle.
- (4) To determine the pharmacokinetics of sublingual CBD

We will record pain medication usage (opioid and non-opioid). Subject reported side effects will also be monitored.

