Randomized subjects will receive either (1) placebo (2) low dose CBD (3) high dose CBD. This study will include an 8-week intervention period during which subjects will be asked to record daily electronic VAS scores, pain medication use and a number of other parameters. They will return at week 12 for a 4 - week post-treatment visit, where they can also choose to enroll in an optional pharmacokinetic study. Participants will complete the Endometriosis Health Profile-30 (EHP-30), Patient Global Assessments (PGAs), and, if partnered and sexually active, the Female Sexual Function Index (FSFI) surveys at 0, 4 and 8, 12 weeks as well as the Patient Global Impression of Change (PGIC) surveys at 4, 8, and 12 weeks. Patients will also have bloodwork done at weeks 0, 4, 8, 12 to assess for circulating markers of inflammation. At week 8, this bloodwork will include circulating CBD levels to assess for steady state concentrations. We will perform bloodwork to assess for possible side effects e.g. liver dysfunction throughout the study duration. Please refer to Section 7.2 Study Procedures for timing and test.

Subjects will be screened for side effects and asked to record pain medication use throughout the duration of the study. At each visit, subjects will be dispensed a 4 week supply of medication **(NETA and CBD)** from the Investigational Pharmacy. They will be required to bring medication bottles to each visit to verify drug accountability. Oxycodone (if prescribed) and NETA pills will be counted and recorded. Additional refills will be provided as needed. The study drug bottle will be inspected and returned to the clinician. The patient will be provided with a new supply of study drug at Visit 3. All NETA and study drug will be returned at the completion of the study.

At the completion of the study, all subjects will be offered the opportunity to do pharmacokinetic testing with sublingual CBD until a maximum number of 4 patients are enrolled. We plan for a total of 3-4 patients. This will be entirely voluntary and they will be compensated appropriately for their time. The testing will include 24 hours of monitoring with sequential blood draws to determine the pharmacokinetic parameters of sublingual CBD after administration and one salivary pH. They will be discharged at 24 hours and asked to return to the clinic at 48 hours for one final lab draw. We will stop recruitment once we have achieved the desired number of participants.

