7.2.5 Study Visit 4 – 8 week treatment

The subject will return in 4 weeks. Again, the study visit window will be 3 days before or 3 days after this time to account for weekends. At this time the subject will be given time to ask any questions or voice any concerns they may have had over the past 4 weeks, reviewing and recording any adverse events. The subject's compliance with daily surveys and the medication will be reviewed as described above in Section 7.2.3. Physical assessment will be formed as outlined in 7.2.3.

No additional medication will be provided at this visit. The patient's will be asked to complete additional surveys: (1) EHP-30 (2) PGA (3) PGIC (4) C-SSRS (5) FSFI (if partnered and sexually active). We will collect bloodwork: (1) Inflammatory markers (2) Monitoring LFTS (3) steady

state plasma concentration of CBD (4) CBC, BMP. This will be approximately 10-15cc of blood or 2-3 teaspoons. The time of their previous dose will be recorded for reference. Please see 7.2.6 for additional details on the pharmacokinetics and determination of CBD levels.

They will be required to bring all medication bottles to the visit. Oxycodone, if prescribed, and NETA pills will be counted and recorded. All unused rescue oxycodone, NETA, and unused study drug will be required to be returned at this visit for accountability purposes. Unused oxycodone will be returned to the subject. Unused NETA and unused study drug will be to Investigational Drug Services and dispensed of appropriately.

The subject will be advised to stop the study drug. If the patient would like to continue NETA for management of endometriosis pain, they will be referred to their primary OB/GYN for management of this medication.

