7.2.6 Study Visit 5 – 12 week (4 weeks post treatment)

The subject will return in 4 week. The study visit will be 3 days before or 3 days after this time to account for weekends. At this final study visit, we will collect final routine bloodwork (1) LFTs (2) inflammatory markers in addition to another urine toxicology and urine pregnancy test. This is be approximately 5-10cc of blood or 1-2 teaspoons. We will complete final surveys 1) EHP-30 (2) PGA (3) PGIC (4) C-SSRS (5) FSFI (if partnered and sexually active). Physical assessment will be performed as outlined in 7.2.3.

If the subject has any abnormal test results or adverse events, these will be followed until their resolution at time intervals deemed appropriate by the clinical team. If there is an unforeseen pregnancy, the pregnancy will be followed throughout for adverse maternal, fetal and neonatal outcomes.

7.2.7 (Optional) Study Visit 6 (Eligibility window: 12-24 weeks post-enrollment)

At the initial enrollment visit, all subjects will be offered participation in the optional pharmacokinetic testing. If interested, they will complete consent during the main consent process and we will recruit until we have enrolled four participants and they have completed this Visit. As we are recruiting from the study participants, who will have already undergone rigorous screening throughout the initial study, we will not be repeating any additional testing on these patient. During this part of the study, they will also only be receiving a one-time dose of CBD. They will remain eligible to participate in this study for up to 3 months from the date of their last visit.

After completion of the initial study, the participants will undergo a 4 week washout period of the study drug, which will correspond with Visit 5 (4 week post-treatment visit).

At this time, screening measures have been set forth by the institution to test for SARS-CoV2 (the virus that causes COVID-19) if a study participant is planning to stay overnight at the Clinical Research Center.

The subjects will be screened via telephone prior to testing.

- If negative, they will proceed to testing.
- If positive, they can be rescreened in 1 or more weeks. If negative, they can proceed to testing. This can continue until the participant is no longer eligible for this portion of the study.

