8.3 Statistical methods

The statistical methods will primarily be descriptive given the sample size and intent of the study.

The primary study endpoint of daily pain (as measured using VAS) will be compared between groups using the area under the curve over the course of the 8-week intervention period. Subsequently, the AUC VAS score data will be normalized per participant to an average AUC VAS score per week (i.e., 7 days) to account for participants that withdraw early from the study. It is well described that endometriosis pain has a cyclic and not a linear pattern. This makes the use of averages and means less useful for monitoring progression of pain. The area under the curve of plots of daily pain should capture endometriosis "flairs" and cyclic pain allowing more accurate comparison between study groups.

We will account for the use of rescue analgesics in the efficacy analysis of CBD and ERP. We will adjust the pain score for analgesic use during the intervention. We will take into account that ERP is often cyclical.

We will compare changes from baseline in secondary study endpoints such as quality of life (QOL) and sexual function as assessed via validated surveys and inflammatory cytokines. We will compare these findings across treatment arms.

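### The FSFI is tied to being partnered and sexually active with no reference date, so the Aim 3 change comparison may be made in a subset that treatment can alter

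*Combined protocol and SAP*

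**What the plan says.** Section 7.1 sets the FSFI timing and attaches the condition to the whole series: "if partnered and sexually active, the Female Sexual Function Index (FSFI) surveys at 0, 4 and 8, 12 weeks". The visit procedures then restate it after randomisation, at week 4 (section 7.2.4, "FSFI (if partnered and sexually active) on-site prior to being discharged from the visit"), week 8 (section 7.2.5, "5) FSFI (if partnered and sexually active). We will collect bloodwork") and week 12 (section 7.2.6, "5) FSFI (if partnered and sexually active). Physical assessment will be performed"). The schedule table in section 7.2 lists the FSFI beside the EHP-30 and PGA at the same four visits and adds no rule.

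The target population is worded in the present tense. Aim 3 in section 1.1 has the FSFI "to be administered to participants with current sexual partners that are sexually active", and section 1.3 names the endpoint as the impact on "sexual function among participants that are currently partnered and sexually active". Neither gives a reference date or a look-back window.

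On analysis, section 8.3 says: "We will compare changes from baseline in secondary study endpoints such as quality of life (QOL) and sexual function as assessed via validated surveys", and adds that findings will be compared across arms. It has no rule for a woman who starts or stops sexual activity after randomisation.

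**The concern.** Sexual activity at weeks 4 and 8 is observed after randomisation, and the protocol itself gives reasons why treatment could change it. Section 2.1 lists dyspareunia among the primary symptoms, section 3.1 requires moderate to severe pain at entry, and section 11.2 expects that CBD may reduce pain and improve sexual function.

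If status is judged at each visit, two groups leave the FSFI change comparison. A woman who stops sexual activity because of pain has a baseline score but no follow-up score. A woman who resumes has a follow-up score but no baseline. Both events bear directly on Aim 3. The women left in each arm are then no longer the groups formed by randomisation, and a difference in mean change mixes any drug effect with a difference in who remains. Sections 2.2 and 8.2 say the results will serve as preliminary data and inform the size of later studies, so a selected FSFI change could be carried forward.

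**Working it through.** **Plan's own figure.** Section 8.1 gives 36 randomised. With 1:1:1 allocation (section 7.2.3) and the rule of 12 cited in section 8.2 applied per arm, 3 × 12 = 36, which reproduces. The documents give no figure for the FSFI subset: no share sexually active, no FSFI SD and no correlation. Everything below therefore rests on assumptions.

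**Step 1. Size of the subset and its sampling error.** Women per arm with a change score = 12 × (share active at baseline) × (share of those still active). The 95% half-width for a two-arm difference, in SD units, is 1.96 × √(2/n).

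| Active at baseline | Still active | n per arm | Half-width (SD) |
|---|---|---|---|
| 50% | 70% | 4.2 | 1.35 |
| 65% | 85% | 6.6 | 1.08 |
| 80% | 100% | 9.6 | 0.89 |
| all 12 scored | – | 12 | 0.80 |

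These use the normal multiplier; a t multiplier would widen them.

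**Step 2. Worst-case selection.** Assume 8 women in an arm are active at week 0, their changes are normal, and the women who become inactive are exactly those with the lowest changes. For n = 8 the three lowest expected order statistics are −1.424, −0.852 and −0.473. The full-sample expectation is 0, so the remaining women's mean rises by:

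- lowest 1 lost: 1.424 / 7 = 0.20 SD
- lowest 2 lost: (1.424 + 0.852) / 6 = 0.38 SD
- lowest 3 lost: (1.424 + 0.852 + 0.473) / 5 = 0.55 SD

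If the other arm keeps all 8, the half-width 1.96 × √(1/8 + 1/n) for n = 7, 6 and 5 is 1.01, 1.06 and 1.12 SD. Even the worst case lies well inside the sampling error.

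**Step 3. Weaker dependence, same scenario.** If becoming inactive is correlated r with change, the shift is r times the figures above. For r from 0.3 to 0.7 this gives 0.06–0.14, 0.11–0.27 and 0.16–0.38 SD for 1, 2 and 3 women.

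**Step 4. A softer model.** Treat sexual function and the tendency to be active as jointly normal, with no drug effect on function. Assume 65% are active at baseline in both arms and, at week 8, 50% are active on placebo and 80% on CBD. Require activity at both visits. In a simulation of 2,000,000 women, the CBD-minus-placebo difference in mean change was as follows, in units of the single-visit score SD:

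| Function–activity correlation | Within-woman correlation 0.5 | Within-woman correlation 0.7 |
|---|---|---|
| 0.3 | −0.07 | −0.04 |
| 0.5 | −0.12 | −0.07 |
| 0.7 | −0.17 | −0.11 |

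At a within-woman correlation of 0.5 the SD of change equals the single-visit SD, since √(2 × (1 − 0.5)) = 1. At 0.7 it is √(2 × 0.3) = 0.77, so −0.04 and −0.11 become about −0.05 and −0.14 in change-SD units. If the two arms have the same activity at week 8, the bias in this model is zero.

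**The case against.** **Timing of the status.** No sentence says that status is reassessed at each visit. Section 7.1 puts one condition on the whole series, Aim 3 can be read as describing a type of participant, and the schedule table carries no condition. A subset defined once is therefore a possible reading. A reader might infer that the protocol expressly prescribes visit-by-visit selection; it does not. The restatement at weeks 4, 8 and 12 and the present-tense endpoint wording make that reading the natural one. If baseline status was meant, the text still needs to say so.

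**Size.** A reader might apply the truncated-normal formula φ(z)/(1 − p) for p = 1/8, 2/8 and 3/8 and quote 0.24, 0.42 and 0.61 SD. That formula is for an infinite population and overstates the shift for eight women. Even 0.20, 0.38 and 0.55 need perfect dependence in one arm only. Sampling error is larger than any of these figures.

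**Weight.** This is a secondary endpoint in a pilot with no power calculation and mainly descriptive methods, and the primary VAS endpoint is untouched. PGA and PGIC are given without the activity condition, and section 1.3 says they cover dyspareunia, so women who stop sexual activity are not lost from every measure. All of this stands and limits the weight of the point. It does not remove it: an interval shows the noise, but selection stays invisible unless activity status is recorded.

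**Measurement.** Limiting the FSFI to sexually active women is a deliberate choice, and scoring inactive women is debatable. That also stands, and it is why the result should be shown both ways.

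**Conclusion.** The point holds as a gap in the definition of the FSFI analysis population. No reference date is given for being partnered and sexually active, and on the natural reading the Aim 3 change comparison is conditioned on a post-randomisation state that treatment may alter.

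Under assumptions the documents do not supply, the shift is at most about 0.20, 0.38 or 0.55 SD when exactly the worst 1, 2 or 3 of 8 women in one arm are lost. It is about 0.04 to 0.17 SD in the softer model, and zero there if activity is equal across arms. Against a half-width of about 0.9 to 1.35 SD this is small.

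A reader might go further and infer that the plan will hide a real benefit, or that it could manufacture one. The documents support neither. They give no information on how activity will differ by arm. In the models above the bias runs against CBD only if CBD keeps more women active. The change is worth making because it is cheap and makes any selection visible, not because the FSFI result is shown to be wrong.

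**What to change.** - **Analysis set.** Define the FSFI change set once, as women partnered and sexually active at week 0, and state a look-back window. Give them the FSFI at weeks 4, 8 and 12 whatever their current activity, and analyse by randomised arm.
- **Inactivity.** State in section 8.3, before unblinding, how responses indicating no activity are handled. Present the FSFI comparison both with and without those women.
- **Companion outcome.** A week-0 set still omits women who resume activity. Ask every woman at every visit whether she is sexually active and, if not, whether pain is the reason. Report this by arm as a companion Aim 3 outcome.

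The cost is wording in sections 1.1, 1.3, 7.1, 7.2.4 to 7.2.6 and 8.3, plus a few questionnaire items at existing visits. No extra visits or participants are needed. The set stays small: with 50 to 80% active at baseline it is 6.0 to 9.6 women per arm, a half-width of 1.13 to 0.89 SD. The FSFI result may also depend on how inactivity is handled, which the two presentations would show.

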7.2.5 Study Visit 4 – 8 week treatment

The subject will return in 4 weeks. Again, the study visit window will be 3 days before or 3 days after this time to account for weekends. At this time the subject will be given time to ask any questions or voice any concerns they may have had over the past 4 weeks, reviewing and recording any adverse events. The subject's compliance with daily surveys and the medication will be reviewed as described above in Section 7.2.3. Physical assessment will be formed as outlined in 7.2.3.

No additional medication will be provided at this visit. The patient's will be asked to complete additional surveys: (1) EHP-30 (2) PGA (3) PGIC (4) C-SSRS (5) FSFI (if partnered and sexually active). We will collect bloodwork: (1) Inflammatory markers (2) Monitoring LFTS (3) steady

state plasma concentration of CBD (4) CBC, BMP. This will be approximately 10-15cc of blood or 2-3 teaspoons. The time of their previous dose will be recorded for reference. Please see 7.2.6 for additional details on the pharmacokinetics and determination of CBD levels.

They will be required to bring all medication bottles to the visit. Oxycodone, if prescribed, and NETA pills will be counted and recorded. All unused rescue oxycodone, NETA, and unused study drug will be required to be returned at this visit for accountability purposes. Unused oxycodone will be returned to the subject. Unused NETA and unused study drug will be to Investigational Drug Services and dispensed of appropriately.

The subject will be advised to stop the study drug. If the patient would like to continue NETA for management of endometriosis pain, they will be referred to their primary OB/GYN for management of this medication.

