7.2.2 Study Visit 1: Screening Visit

Pre-screening will take place in the Penn State Hershey MIGS clinic or over the phone with women identified as potential candidates for study participation via prior clinic visits. If the subject meets all pre-screening criteria, she will return for a screening encounter and undergo informed consent prior to any study procedure. The subject will be given ample time to ask questions or voice concerns about the study.

A detailed history and physical exam will be performed, particularly to assess for concomitant use of anti-epileptic drugs and or underlying risk of liver dysfunction. We will need approximately 8-10 cc of blood (approximately 2 teaspoons).

- 1. Liver function tests (LFTs) will be drawn.
- 2. Baseline CBC and BMP will be drawn.
- 3. Screening urine toxicology will also be performed to confirm no recent THC use.
- 4. Urine pregnancy test will be collected.
- 5. Pain medication and narcotic usage from the prior month will be assessed.
- 6. Suicidal ideation will be assessed via the Columbia-Suicide Severity Rating Scale (C-SSRS).

If the subject is found to be pregnant, have evidence of underlying hematologic/ urologic/ hepatobiliary dysfunction or a positive urine toxicology for recent THC use, the subject will be excluded.

Current medication usage will be reviewed thoroughly with special attention paid to Cytochrome P450 (CYP) inducers and inhibitors as well as Substrates of uridine 5'-diphosphoglucuronosyltransferase (UGT). If the subject is screened into the study, their condition and corresponding medication will be recorded throughout the study. Please refer to Section 10 Risks, Drug Interactions, for additional guidelines.

Baseline survey data will be collected and entered into the RedCap secured database. This information will include the WERF EPHect Questionnaire.

At this time subjects will be set up for emails to complete VAS scores directly into RedCap. If not done already, the subject will be transitioned to norethindrone acetate to start taking immediately and given instruction on how to complete the VAS scores and study questions. It will be explained to the patient that she must complete 5 out of 7 days of surveys to be enrolled into the study. If the subject is unable to complete the 5 out of 7 days, the subject will be given one additional week to determine if compliance is attainable. If the subject is unable to do so, they will screen fail.

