7.2.3 Study Visit 2 – Enrollment Visit

The subject will be scheduled for a randomization/enrollment 1-2 weeks after the screening visit. The randomization will be double blind and 1:1:1. The patient will have been expected to be on norethindrone acetate (NETA) for 30 days prior to the enrollment visit. Dosing for norethindrone acetate will start at 5mg oral daily, but may be adjusted from 2.5 mg to 15 mg depending on the subject's needs to achieve amenorrhea as this standard treatment for endometriosis or to increase compliance by reducing side effects. The study team will be responsible for adjusting dosages at subsequent study visits 3 and 4. At this visit, the subject will be randomized into Group A, Group B, Group C by IDS as long as the subject has met all the criteria for enrollment. The groups are listed below:

Group	Treatment
А	Norethindrone acetate + Placebo (Hemp Seed Oil)
В	Norethindrone acetate + low dose CBD (10mg sublingual daily)
С	Norethindrone acetate + high dose CBD (20mg sublingual daily)

The subject will be given a 4 week supply of (1) placebo (2) low dose CBD or (3) high dose CBD product and instructed on its application. The subject will also receive a 4 week supply of norethindrone. Refer to the following:

- a. In the morning, take the norethindrone acetate orally with a sip of water at approximately the same time each day. This can be taken on an empty or full stomach.
- b. Prior to bed, you will administer the study drug.
 - 1. Please refrain from eating (drinking is permissible) 60 minutes prior to administration.
 - 2. Place 4 drops of the study drug under your tongue.
 - 3. Hold the study drug under the tongue for 60 seconds. After that time, swallow any remaining drug.
 - 4. Repeat steps 2 and 3 for a total of 8 drops.

Please avoid eating, drinking or smoking for 2 hours after administration.

A focus group was conducted to determine the optimal route of administration of the study drug. 1 application of 8 drops of the study drug versus 2 applications of 4 drops were compared and it was determined that the latter method was preferred.

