7.3 Duration of Participation

Study participation is expected to be 13-14 weeks. For those who participate in the optional PK study, participation may extend to 12-24 weeks post-enrollment.

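### CBC and BMP are scheduled only at screening and at the visit where study drug stops; adding them to the existing week-4 draw is a cheap, minor safety improvement

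*Combined protocol and SAP*

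**What the plan says.** The schedule table in section 7.2 marks CBC and BMP at two visits, and the visit descriptions show which two.

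- **Visit 1 (section 7.2.2):** "Baseline CBC and BMP will be drawn".
- **Visit 2 (section 7.2.3):** inflammatory markers only.
- **Visit 3 (section 7.2.4):** "The following bloodwork will be obtained: (1) Inflammatory markers (2) Monitoring LFTS". The volume is given as "Approximately 1-2 teaspoons of blood will be drawn at this visit". A further month of study drug is handed out here.
- **Visit 4 (section 7.2.5):** inflammatory markers, LFTs, the CBD level, and CBC with BMP; the list ends "state plasma concentration of CBD (4) CBC, BMP". No more drug is supplied, and "The subject will be advised to stop the study drug".
- **Visit 5 (section 7.2.6):** LFTs and inflammatory markers.

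Three other places bear on this schedule. Section 10 includes lower haemoglobin and haematocrit, and a reversible rise in creatinine, among the less common effects of CBD. For drug interactions, section 10 declines to adjust doses. It relies on adverse-event checks at visits, routine bloodwork and removal under section 3.3.1. Section 3.3.1 withdraws women who reach CTCAE Grade 3 if the event is attributable to study drug, treats undetermined causality as attributable, and gives anaemia with haemoglobin below 8.0 as an example.

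**The concern.** The protocol names two laboratory effects and has a removal rule that could act on them. For a woman without symptoms, however, it schedules no measurement of either analyte between the first dose and the visit at which dosing ends. The haemoglobin example in section 3.3.1 can be applied only with a haemoglobin value. By the time one is scheduled, removal can no longer spare her any study drug.

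The liver is handled differently: the week-4 LFTs allow the liver criteria to be applied with about half of the dosing period left. Bloodwork is also part of the stated protection against interactions. Section 10 warns that moderate or strong CYP3A4 or CYP2C19 inhibitors may raise CBD levels, and section 3.2 does not list those inhibitors as exclusions.

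What is at stake is avoidable exposure for an individual woman. No effect on the VAS endpoint or on any secondary endpoint is claimed.

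**Working it through.** **Inputs.** Visits 3 and 4 are at 4 and 8 weeks, each within 3 days (section 7.2 table). The run-in comes from section 7.2.3: "The subject will be scheduled for a randomization/enrollment 1-2 weeks after the screening visit". Study drug is taken for up to 8 weeks (section 7.4.2). Planned enrolment is 36 (section 8.1). Day 0 is Visit 2.

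**The plan's own total.** A run-in of 1-2 weeks plus 12 weeks to Visit 5 gives 12 + 1 = 13 to 12 + 2 = 14 weeks. Section 7.3 agrees: "Study participation is expected to be 13-14 weeks".

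**Visit days.**
- Visit 3: 28 - 3 = 25 to 28 + 3 = 31.
- Visit 4: 56 - 3 = 53 to 56 + 3 = 59. If the Visit 4 window is instead counted from the actual date of Visit 3, the range is 25 + 25 = 50 to 31 + 31 = 62. The conclusion does not change.

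**Scheduled results after the first dose and before Visit 4.** CBC/BMP: 0. LFTs: 1, at Visit 3.

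**Interval from the screening CBC/BMP to the next one.**
- As planned: 7 + 53 = 60 to 14 + 59 = 73 days.
- With a panel at Visit 3: 7 + 25 = 32 to 14 + 31 = 45 days.

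Both intervals include the 7-14 undosed run-in days, so they describe time between samples and not exposure. Both lengthen if a second run-in week (section 7.1) delays enrolment.

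**Dosing still avoidable after a Visit 3 sample.**
- Least: late Visit 3, early Visit 4: 53 - 31 = 22 days.
- Most: early Visit 3, dosing to the 8-week cap: 56 - 25 = 31 days.

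Window days 57-59 are not counted, because dosing is capped at 8 weeks (day 56). A 4-week supply is dispensed at Visit 3, so the practical figure is nearer 28 days unless bottles are overfilled. Laboratory turnaround reduces all of these figures.

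**Cost.**
- Panels: 36 women x 1 = up to 36.
- Blood: Visit 3 is 1-2 teaspoons, about 5-10 mL at 5 mL per teaspoon. For Visit 4, "This will be approximately 10-15cc of blood or 2-3 teaspoons". The difference is 10 - 5 = 5 to 15 - 10 = 5 mL. This is an upper bound, because the Visit 4 volume also covers the CBD level.
- One removal from an arm of 36 / 3 = 12 is 1/12, about 8% of that arm.

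**The case against.** The strongest reply is that the schedule is already proportionate to the risk. LFTs, the main laboratory concern, are checked at weeks 4, 8 and 12, and effects described as less common are tested at baseline and at the end of dosing. For a week-4 count to trigger the Grade 3 rule, several things must coincide:

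- A woman who passed screening for haematologic dysfunction must fall below 8.0 within about 4 weeks at 10-20 mg/day.
- She must have none of the symptoms she was told to act on, such as breathlessness or persistent dizziness.
- The Visit 3 vital signs, review of systems and directed examination must reveal nothing.

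The documents give no evidence that this happens. A smaller fall would not meet the Grade 3 rule and would leave only the investigator's discretion under section 3.3.1.

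That stands, and it is why the severity is minor. Other safeguards also narrow the gap: norethindrone is titrated toward amenorrhea, diaries record bleeding, and abnormal results are followed to resolution (section 7.2.6). None of them measures haemoglobin or creatinine during dosing.

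Some stronger readings are tempting but unsupported:

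- *The protocol breaks a promise to check blood throughout.* Section 7.1 leaves the timing to section 7.2, and the scheduled LFTs count as routine bloodwork.
- *These changes would go undetected.* Visit 4 can find them, and women with symptoms can be identified earlier. What is missing is a scheduled result in time to spare dosing.
- *Section 3.3.1 sets a creatinine threshold.* It names none; only its general Grade 3 clause could apply, and section 10 calls the rise reversible.
- *The mg/kg doses in section 10 show how large or small this risk is.* Those figures concern transaminases after oral dosing. They do not measure haemoglobin or creatinine effects of a sublingual product.

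**Conclusion.** The point holds as a cheap improvement of minor severity. There are 0 scheduled CBC/BMP results between the first dose and Visit 4, so the Grade 3 removal rule has no scheduled result to act on for a symptom-free haemoglobin or creatinine change during dosing. A Visit 3 panel would supply one, with about 22-31 dosing days still avoidable before laboratory turnaround.

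This rests on the stated visit windows, the 8-week dosing cap and a 1-2 week run-in. The schedule fact is certain, since table and visit text agree. The benefit is small and cannot be quantified: the documents give no rate for either effect and no dose at which it occurred.

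**What to change.** Add CBC and BMP to the blood already drawn at Visit 3, and review the result against section 3.3.1 when it returns. Amend the schedule table in section 7.2, the Visit 3 blood list in section 7.2.4 and the blood volume stated there. Visits 5 and 6 need no change.

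The cost is up to 36 extra panels, about 5 mL more blood per woman and one minor amendment, with no new visit or needle stick. If Visit 3 is held remotely, the panel depends on whatever arrangement is made for the LFTs.

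There is one trade-off to accept knowingly. Irregular bleeding is a common norethindrone reaction, and undetermined causality is attributed to study drug. A bleeding-related Grade 3 anaemia could therefore lead to early removal, with no further data collected and no replacement (section 3.3.2). Removal may still be right for that woman.
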